4.3.1 Early Termination Study Visit

If a subject withdraws from the study, then their data which has already been collected will remain in the study. If they withdraw after being intubated, the 24 hour post intubation review of records will be done to assure no AE has occurred as a result of the intubation for safety monitoring. However, if subject withdraws prior to being intubated, no further data will be collected and no study procedure will be performed.

5 STUDY EVALUATIONS AND MEASUREMENTS

5.1 Screening and Monitoring Evaluations and Measurements

5.1.1 Medical Records Review

- Demographics including MRN, name, and elements of dates including date of birth at el
 - Birth history including post menstrual age and congenital birth defect et al
 - Medical history and surgical history including diagnosis and any previous intubation history et al
-

- Chart review to collect clinical information up to 24-hour post intubation or upon discharge from PACU
- ASA physical status
- Airway assessment
- Surgical information including procedure date, type of surgical procedure, surgery length et al.
- Anesthesia records including vital signs, oxygen saturation, medications, and notes
- Post intubation assessment including complications associated with intubation

5.1.2 Clinician's Records

- Clinician's clinical role and years of professional experiences
- Experiences of study device intubation on infant

5.1.3 Intubation

- Clinicians' name who perform the intubation
- Number of attempts
- Intubation devices
- Intubation associated complications

5.2 Safety Evaluation

Subject safety will be monitored and treated by per institutional standard clinical of care since the study procedure is institutional standard practice. Any adverse event related to intubation will be recorded on the study Case Report Form (CRF).

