2.2 Secondary Objectives

- Number of attempts for successful intubation
- Frequency of failure to intubate with assigned device
- Frequency of complications such as hypoxemia related to intubation with the two study devices

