3.2 Allocation to Treatment Groups and Blinding

CHOP will be the Data Coordinate Center (DCC). The DCC will generate the randomization sequence by statisticians. The randomization sequence will be maintained in study EDC, a CHOP REDCap registry, by study manager at DCC.

Randomization will be stratified by site and clinician's role at each site with random block sizes of 2, 4 or 6 to ensure equal numbers of VL and DL subjects within each site and type of clinician, and, to avoid predictability of the device. Randomization is only for the first intubation attempt. Any subsequent attempts will be at the supervising clinician's discretion either with the randomized device or an alternate device

Blinding of study device and study staff is not feasible in this study. However, the statisticians will be blinded at the time of data analysis.

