- ID 3.0mm cuffed (birth to < 1 month; >3kg body weight);
- ID 3.5mm cuffed (1 month to < 8 months);
- ID 4.0mm cuffed (8 to 12 months).

If the first attempt at tracheal intubation attempt fails, the device used for subsequent attempts will be at the discretion of the attending anesthesiologist.

A member of the research staff is required to observe the intubation and record the study information.

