8.3 Definition of an Adverse Event

An adverse event is any untoward medical occurrence in a subject who has received an intervention (drug, biologic, or other intervention). The occurrence does not necessarily have to have a causal relationship with the treatment. An AE can therefore be any unfavorable or unintended sign (including an abnormal laboratory finding, for example), symptom, or disease temporally associated with the use of a medicinal product, whether or not considered related to the medicinal product.

All AEs related to the study intervention/intubation will be noted in the study records and on the case report form with a full description including the nature, date and time of onset, determination of non-serious versus serious, intensity (mild, moderate, severe), duration, causality, and outcome of the event.

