9.1.2 Blinding

Blinding of the PI and clinician is not feasible in this study. The statisticians will be blinded at the time of generating the randomization schedule and remain blinded at the time of analysis.

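### Adverse events are recorded when related to intubation, an undefined judgment made by people who know the device, so judgment-dependent complications could differ between arms through attribution

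*Combined protocol and SAP*

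**What the plan says.** The recording rule appears twice. Section 5.2: "Any adverse event related to intubation will be recorded on the study Case Report Form (CRF". Section 8.3: "All AEs related to the study intervention/intubation will be noted in the study records and on the case report form". Section 8.1 limits monitoring in the same way, and the chart review in Sections 3.1.2.3 and 4.2.4 looks for events with the same qualifier.

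The definition in Section 8.3 is wider. Of an adverse event it says: "The occurrence does not necessarily have to have a causal relationship with the treatment". The same section then asks for causality on the events already selected as related.

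On who knows the device, Section 3.2 says "Blinding of study device and study staff is not feasible in this study" and Section 9.1.2 says "Blinding of the PI and clinician is not feasible in this study". Section 4.2.3 adds: "A member of the research staff is required to observe the intubation and record the study information". The one blinding measure is that "the statisticians will be blinded at the time of data analysis".

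The comparison concerned is a secondary objective in Section 2.2: "Frequency of complications such as hypoxemia related to intubation with the two study devices".

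Other data are listed with no relatedness condition: number of attempts, vital signs, oxygen saturation, medications and notes (Sections 4.2.4, 5.1.1 and 5.1.3). Those sections also list complications associated with intubation. The only complication whose analysis is named, in Section 6.3.2, is lowest oxygen saturation.

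**The concern.** A comparison of complication frequency is sound only if an event has the same chance of being counted in each arm. Here an undefined relatedness judgment comes before recording, and those making it know which laryngoscope was used. Around induction, laryngospasm, bronchospasm or minor airway trauma can be put down to the device, the drugs or the infant. If the habit of attribution differs by device, the recorded rates differ even when the true rates do not. Blinding the statisticians does not help, because they see the data after events have been selected.

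At stake is part of a secondary objective. It matters because Section 1.1 presents fewer complications as the purpose of reducing attempts, and states an expectation about which device will do better.

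**Working it through.** **Is there a plan figure to reproduce?** The plan gives no complication rate, power or sample size for this comparison. The only plan figure used below is the arm size, so that was checked first.

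- Two proportions, 84% vs 94%, two-sided 5%, 80% power, unpooled variance: (1.960 + 0.842)² × (0.84×0.16 + 0.94×0.06) / 0.10² = 149.8 per arm.
- Times the standard two-look Pocock inflation factor, 1.110: 166.2, rounded up to 167 (Section 6.4: 167).
- 167 / 0.90 = 185.6, rounded up to 186 (Section 6.4: 186).
- 186 × 1.45 = 269.7, rounded up to 270 (Section 6.4: 270).

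**Which events pass through the filter?**

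| Outcome | Source in the plan | Depends on relatedness? |
|---|---|---|
| First-attempt success, number of attempts | Observed and recorded for each intubation | No |
| Lowest oxygen saturation | Anesthesia record | No |
| Hypoxemia, bradycardia | Charted saturation and vital signs, if derived by a fixed rule; no rule is given | Avoidable |
| Laryngospasm, bronchospasm, airway trauma | Adverse-event recording; perhaps the associated-complications items | Yes under Sections 5.2 and 8.3; not stated for the other items |

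The concern is confined to the last row, and to the third row if those events are counted from adverse-event forms.

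**Illustration of the mechanism.** Inputs: 270 per arm; the same true rate in both arms, either 20% (any complication in children in the earlier multicenter study cited in Section 1.1) or 10% (assumed); probability of being judged related 90% in one arm and 90%, 80%, 70% or 60% in the other (all assumed). Clustering and losses are ignored.

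Recorded rate q = true rate × probability judged related. With d = q₁ − q₂ and p̄ the mean of q₁ and q₂, se₀ = √(2p̄(1−p̄)/n) and se₁ = √((q₁(1−q₁) + q₂(1−q₂))/n). The chance of p<0.05 is Φ((d − 1.96se₀)/se₁) + Φ((−d − 1.96se₀)/se₁).

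Worked case, 20% with 90% vs 70%: q₁ = 0.18, q₂ = 0.14, d = 0.04, p̄ = 0.16; se₀ = √(0.2688/270) = 0.03155; se₁ = √(0.2680/270) = 0.03151. The first term is Φ(−0.69) = 0.244 and the second is below 0.001, giving 24.5%.

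| True rate | Judged related | Recorded | Odds ratio | Chance of p<0.05 |
|---|---|---|---|---|
| 20% | 90% vs 90% | 18% vs 18% | 1.00 | 5.0% |
| 20% | 90% vs 80% | 18% vs 16% | 0.87 | 9.5% |
| 20% | 90% vs 70% | 18% vs 14% | 0.74 | 24.5% |
| 20% | 90% vs 60% | 18% vs 12% | 0.62 | 49.7% |
| 10% | 90% vs 80% | 9% vs 8% | 0.88 | 7.0% |
| 10% | 90% vs 70% | 9% vs 7% | 0.76 | 13.7% |
| 10% | 90% vs 60% | 9% vs 6% | 0.65 | 26.2% |

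Equal attribution does no harm to the error rate; unequal attribution does. The 20% rate covers all complications, not only the judgment-dependent ones, so it should not be read as the expected rate for those events in this trial.

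**The case against.** The strongest reply is that the adverse-event rules are not the only route. Sections 4.2.4, 5.1.1 and 5.1.3 list associated complications, and association can be purely temporal. A research observer attends each intubation, and the form, which is not among the documents, may already be a checklist. This largely stands. A reader might infer that complications reach the form only through a causal judgment, or that an event judged unrelated is lost for good. The documents do not support either: vital signs, medications and notes are also collected. But nothing says the associated-complications items are filled in regardless of judged cause, and recovering a brief laryngospasm from notes depends on someone having written it down.

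A second reply is that related may simply mean occurring around intubation, since Section 8.3 asks for causality separately and that field would otherwise be nearly redundant. That reading is possible, but it is not stated, and different sites could read the rule differently.

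Third, the objective itself concerns complications related to intubation, so the restriction partly follows the stated target. That is a reason to keep a related-only analysis, not to select events before they are recorded.

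Fourth, Section 1.1 centers the complication hypothesis on hypoxemia, and Section 6.3.2 names lowest saturation. This stands: the most prominent complication measure lies outside the mechanism. For the same reason, the illustrated gaps should not be set against the hypoxemia difference implied by Section 1.3.

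Finally, the attribution splits are assumed, and the 20% comes from a different population. That stands too.

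**Conclusion.** The concern holds in a limited form. The recording rule in Sections 5.2 and 8.3 is narrower than the definition in Section 8.3, has no criteria, and is applied by people who know the device. The comparison of laryngospasm, bronchospasm, airway trauma and similar judged events is therefore open to differential attribution. First-attempt success and lowest oxygen saturation are not.

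No size can be claimed for this trial. Under the assumptions shown, the chance of a spurious significant difference runs from 7.0% (10% rate, 90% vs 80%) to 49.7% (20% rate, 90% vs 60%), and stays at 5% if attribution is equal. A reader might infer that the plan will produce a false advantage for VL. The documents do not show that attribution would differ, nor in which direction. This is a weakness in a secondary comparison that can be removed cheaply, not evidence of a biased result.

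**What to change.** In Sections 3.1.2.3, 4.2.4, 5.2, 8.1 and 8.3:

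- Record for every subject each event on a fixed list with written definitions: the events named in Section 1.1 (hypoxemia, esophageal intubation, laryngospasm, bronchospasm, cardiac arrest, airway trauma) plus bradycardia. Do so whatever the judged cause, within one stated peri-intubation window.
- Derive hypoxemia and bradycardia from the charted values by a fixed rule.
- Keep relatedness as a separate field. Compare arms on all listed events, and use the related-only subset as a sensitivity analysis.
- State that the associated-complications items in Sections 4.2.4, 5.1.1 and 5.1.3 follow the same rule, so that recording and definition agree.
- For later events found by chart review, reconcile the 24-hour limit with the alternative of PACU discharge in Sections 4.2.4 and 5.1.1. A peri-intubation window separate from this review keeps unrelated postoperative events out of the main comparison.

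The cost is slightly more data entry by the observer and chart reviewer already planned, and some unrelated events adding noise to both arms alike. The change does not remove unblinded judgment of whether an event occurred; written definitions only reduce the room for it.

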6 INVESTIGATOR STATISTICAL CONSIDERATIONS

6.1 Primary Endpoint

The primary aim is to determine the proportion of tracheal intubation success on first attempt of VL compared to DL. The primary endpoint is the successful tracheal intubation at first attempt. The first-attempt success of intubation will be coded as a dichotomous variable (success=1, nonsuccess=0). As a comparative effectiveness study, the treatment procedure will be randomly assigned to participants after consent is obtained in a two-arm, parallel design. If warranted, we will use a logistic regression model in the mixed model framework to allow for the inclusion of multi-level effects for individuals nested within sites and site-specific effects such as staffing, caseload, experience of staff, etc. In this analysis, we can address systematic effects that possibly lead to different success rates between sites, and/or clinicians, without compromising the integrity of the randomization procedure. Although the main interest is in successful intubation, secondary aims can also be investigated through the logistic regression mixed models approach.

6.2 Secondary Endpoint

The secondary endpoint is successful tracheal intubation.

6.3 Statistical Methods

6.3.1 Baseline Data

Baseline and demographic characteristics will be summarized by standard descriptive summaries (e.g. means and standard deviations for continuous variables such as age and percentages for categorical variables such as gender). To test the difference of demographic variables between treatment groups, student's t-test or Wilcoxon test will be used for continuous variables, while Chi-square test, or Fisher's exact test will be used for categorical variables. Comparisons of demographic characteristics between the sites will be accomplished by reporting effect size measurements (i.e., Cohen's d, phi-coefficient, odds ratios) between each site as a descriptive analysis of differences at baseline.

6.3.2 Statistical Analysis

The study is powered for the primary outcome: successful tracheal intubation on first attempt. Assuming that a 10% increase in successful tracheal intubation (i.e., intubation on first attempt) is clinically meaningful, and that a reasonable rate for baseline success is (84%) (Based on our single center data) an overall sample size of 540 randomly assigned to VL or DL, will provide approximately 80 % power at the nominal two sided 5% level of significance. This calculation accounts for approximately 10% withdrawal, dropout, missing data and other data quality issues. We assume the success rate will be similar across sites. The statistical package SAS's module: PROC SEQDESIGN, was used for the sample size determination. The order of assignment of intubation method (VL vs. DL) for patients intubated by the same clinician will be done using blocked randomization with block sizes of 2, 4 or 6. The primary analysis will be based on intention-to-treat approach and include all the randomized subjects. Logistic regression will be used to compare first-attempt success proportion of tracheal intubation between DL and VL. To adjust for clinician-level clustering of outcome variable, we will apply generalized estimating equations (GEE) method to the logistic regression model to get the marginal odds ratio for first-attempt success comparing VL and DL. . We will include the patient characteristics: ASA status, thyromental distance and weight (less than 10kg, & more than 10kg) as covariates in the logistic regression model. Since there will be an interim analysis the p-value is considered significant if it is less than 0.029 to maintain the overall significance level of the study (Type I error rate) at 0.05^{14} Also, it may be that VL offers greater advantage for those with less experience such as residents as compared to attending physicians or fellows. To assess if there is this effect modification we will include class of clinicians with intervention (DL vs VL) as an interaction term in the logistic regression. In addition, we will analyze the number (not dichotomizing) of intubation attempts using a generalized linear model with the negative binomial distribution. Difference in complications, such as lowest oxygen saturation during tracheal, between treatment groups will be analyzed in multivariate linear models or generalized linear models as appropriate. General linear models and GEE

approach will be used for these models to adjust for site-level and clinician-level clustering of outcome variables.

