Follow-Up	
For clinician participants
 
(1) Screening: identifying anesthesia clinicians from the department list
 
(2) Consent: verbal consent will be obtained
 
(3) Clinical experience data will be collected
 
(4)

Efficacy Evaluations	The primary efficacy endpoint will be successful tracheal intubation
Safety Evaluations	Tracheal intubation by VL or DL are routine standard of care at each participating center. Other than randomization, there is no study intervention that will be introduced to the subjects. Subjects will be monitored per institutional standard practice. Any procedure related AEs will be treated per institutional standard practice.
Statistical And Analytic Plan	We will consider a 10% improvement in first attempt success rate for VL compared to DL to be indicative of a significant clinical effect. The statistical analysis of this change will be based on a logistic regression model where an odds ratio greater than 2.98 will be considered evidence of efficacy of VL compared to DL. The GEE method will be applied to adjust for clinician-level correlation of the outcome variable. There will be an interim analysis when 224 evaluable subjects are enrolled. The proportion of subjects that are successfully intubated at the first attempt will be compared for VL and DL using conditional logistic regression with $\alpha = 0.029$

	used for significance. This more stringent criteria for significance (0.029 instead of 0.05) is Pocock's method of correction for maintaining overall study significance level at 0.05 when there is one interim analysis the overall estimate.
DATA AND SAFETY MONITORING PLAN	Each participating site PI will be responsible for oversight of the study safety. We expect no more than standard clinical risks associated with intubation. There is no DSMB for this study.

FIGURE 1: STUDY DIAGRAM

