6.3.3 Efficacy Analysis

The primary analysis will be based on an intention to treat approach and will include all randomized subjects.

The primary efficacy endpoint will be a successful tracheal intubation following the procedure. We will consider a 10% improvement between VL compared to DL to be indicative of a significant clinical effect. The statistical analysis of this change will be based on a logistic regression model where an odds ratio greater than 2.98 will be considered evidence of efficacy of VL compared to DL. Marginal odds ratios with 95% confidence intervals will be reported for the sample overall, as well as each site, if appropriate.

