6.5 Interim Analysis

There will be an interim analysis after 224 evaluable subjects are enrolled. The proportion of subjects that are successfully intubated at the first attempt will be compared for VL and DL using logistic regression with $\alpha = 0.029$ for significance. This more stringent criteria for significance (0.029 instead of 0.05) is Pocock's method of correction for maintaining overall study significance level at .05 when there is one interim analysis. We will include ASA status, thyromental distance and weight less than 10kg as covariates in the logistic regression. The probability of stopping at the interim analysis (mid-point) is 46.4%, if the true improvement in intubation first attempt success rate is 10.0% (i.e. 84% true first attempt success rate for DL vs. 94% true success rate for VL). However, if the true improvement in first attempt intubation success rate is 12.0% (i.e. 84% vs 96% for DL and VL respectively), then the probability of stopping early increases to 83.0%.

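### Site and clinician role stratify the randomisation but are not named covariates in the final or interim model, and the interim model is named in two ways (minor: efficiency and consistency)

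*Combined protocol and SAP*

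**What the plan says.** **Randomisation.** Section 3.2: "Randomization will be stratified by site and clinician's role at each site". Sections 4.2.2 and 9.1.1 agree, and 4.2.2 justifies the strata as possible predictors of the outcome.

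**Final model.** Section 6.3.2 specifies logistic regression with clinician-level GEE, giving a marginal odds ratio, with "patient characteristics: ASA status, thyromental distance and weight (less than 10kg, & more than 10kg) as covariates". For effect modification it adds: "we will include class of clinicians with intervention (DL vs VL) as an interaction term in the logistic regression".

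**Interim model.** The synopsis says the proportions "will be compared for VL and DL using conditional logistic regression", with no conditioning set. Section 6.5 specifies logistic regression: "We will include ASA status, thyromental distance and weight less than 10kg as covariates in the logistic regression". It does not mention GEE or clustering.

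**Site elsewhere.**
- Section 6.1: "If warranted, we will use a logistic regression model in the mixed model framework", with no criterion for when that applies.
- Section 6.3.3: "Marginal odds ratios with 95% confidence intervals will be reported for the sample overall, as well as each site, if appropriate".
- End of section 6.3.2: the GEE "approach will be used for these models to adjust for site-level and clinician-level clustering of outcome variables". Following the sentences on number of attempts and complications, this most naturally refers to the secondary-outcome models.

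**The concern.** Factors used to stratify the randomisation normally belong in the analysis model. Stratification balances the arms on them, but a model without them does not credit that balance in its standard error. If the factors predict success, the test then runs below its nominal level and loses a little power. Role may well be prognostic, since section 1.1 expects a gap between trainees and experienced laryngoscopists. Section 6.3.2, by contrast, assumes similar success across sites.

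Two specification gaps come with this. A reader cannot tell which model produces the interim p-value that could stop the trial. Nor is it clear whether the role-by-device term sits in the primary model. If it does, the device coefficient is the effect in one reference role, not the overall marginal odds ratio promised in sections 6.3.2 and 6.3.3.

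**Working it through.** **1. The plan's own figures (section 6.4).** Variance term: 0.84 × 0.16 + 0.94 × 0.06 = 0.1908. Fixed-design size: (1.960 + 0.842)² × 0.1908 / 0.10² = 149.8 per group. The two-look Pocock factor of 1.1104 gives 166.3, so 167. Then 167 / 0.9 = 185.6, so 186, and 186 × 1.45 = 269.7, so 270 per group. The plan's numbers reproduce. No covariate enters them, so changing the covariates leaves 540 unchanged. The odds ratio (0.94/0.06) / (0.84/0.16) = 2.98 also reproduces.

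**2. Analytic size of the effect.** Suppose the strata explain 5% of outcome variance, that is, all of the clinician-level share assumed in section 6.4. The true variance of the unadjusted contrast is then 0.95 of what the model reports. The two-sided 0.029 critical value is 2.183.
- Level without strata: 2 × (1 − Φ(2.183/√0.95)) = 0.025 instead of 0.029.
- Signal at 84% vs 94%: 0.10 / √(0.1908/270) = 3.762.
- Power without strata: Φ((3.762 − 2.183)/√0.95) = 94.7%.
- Power with strata: Φ(3.762/√0.95 − 2.183) = 95.3%, a gain of 0.6 points.

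These exceed the plan's 80% because all 270 per group are taken as analysed and no design effect is applied to a device contrast made within clinicians.

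**3. Simulation.** Permuted blocks of 2, 4 or 6 within site by role; 4 or 8 unequal sites and equal role shares (assumed). The between-clinician variance share is 0.05, of which none, half or all is due to the strata (assumed). Tests use a clinician-clustered sandwich at two-sided 0.029, and fits that cannot be estimated count as non-rejections. ASA status, thyromental distance and weight are not simulated, because the plan gives no effects for them.

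| Setting | Without strata | With strata |
|---|---|---|
| Final, null, prognostic strata, 3 patients per clinician (assumed) | 0.024–0.027 | 0.027–0.031 |
| Final, null, 10 per clinician (section 6.4) | 0.032–0.037 | 0.034–0.038 |
| Final, power at 84% vs 94% | 94.3–95.2% | 94.4–95.6% |
| Interim, N = 224, 84% vs 94% (role only) | 57.0–58.1% | 57.4–58.6% |

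With both tests calibrated to 0.029, adding role changes final power by −0.1 to 0.0 points. At 84% vs 96%, power is 99.5–99.6% with or without role.

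The synopsis and section 3.3.2 expect about 500 clinicians for 550 evaluable subjects: 550/500 = 1.1 each, not 10. At 1.1 with strongly prognostic role, the gain is about 0.5 points at N = 540 and 0.5–1 point at N = 224.

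**4. Ordinary logistic regression, as section 6.5 is worded.** With six equal sites, null rejection without strata was 0.020–0.025 at N = 224 and 0.019–0.025 at N = 540. Adding both site and role at N = 224 raised rejection at odds ratio 2.98 from 0.50–0.56 to 0.52–0.61. Not all of that is recovered precision: with no stratum effect at all it still rose from 0.499 to 0.519. Expected interim failures are only 112 × 0.16 + 112 × 0.06 = 24.6. Where inestimable fits count as non-rejections, unpooled site at the interim cost about 9 points.

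**5. The two interim models.** The conditioning set in the synopsis could be site, site by role, or clinician (section 6.3.2 also describes blocked assignment for patients of the same clinician). At N = 224 and 84% vs 94%, with no clinician effect, ordinary logistic regression and regression conditioned on site by role rejected about equally often (0.57–0.59 and 0.56–0.59). They gave opposite stopping decisions in 1.7–5.2% of trials.

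**6. The interaction.** With equal role shares (assumed), a reference role has 270/3 = 90 per arm. If it had the design effect, its signal would be 0.10 / √(0.1908/90) = 2.17 against a critical value of 2.18, so power is about 50%. That would apply only if the primary p-value were read from this coefficient.

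**The case against.** The strongest reply is that adding strata buys nothing under the plan's own assumption. At 10 patients per clinician, null rejection is already slightly above 0.029, adding strata moves it slightly further, and the size-matched gain is nil. The clinician GEE clusters on units nested in site and role and so absorbs most of the effect. Section 6.1 leaves room for a mixed model, and a conventional interaction fit also carries a role main effect. The interim figures in the table use a clinician-clustered variance that section 6.5 does not state.

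Much of this stands, and it is why the point is minor. It does not settle everything. The roughly 500 clinicians expected elsewhere imply small clusters, where the test does run a little below nominal. The section 6.1 option has no trigger. The conflict between the synopsis and section 6.5 is untouched, and the unstated clustering at the interim is itself part of the gap.

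A reader might infer that leaving out the stratification factors inflates the type I error or leaves the trial underpowered. Neither follows. Omission pushes the test toward conservatism. The small excess at 10 patients per clinician is probably a small-sample effect of the uncorrected sandwich with about 54 clinicians (540/10), and it is present with or without the strata. Nor do the documents show that the interaction is meant for the primary model: its stated purpose, effect modification, suggests a separate one.

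**Conclusion.** The point holds as a minor matter of efficiency and consistency. With prognostic strata and few patients per clinician, null rejection is about 0.02–0.027 against 0.029. Adding role gains about 0–1 point of power, and about nil after size calibration at 10 patients per clinician. If the strata are not prognostic, leaving them out costs essentially nothing. The specification gaps matter more than the power: the interim model and its variance, and the place of the interaction, should be settled before interim data are seen.

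The text of the plan establishes the omissions and the conflict with high confidence. The magnitudes rest on assumed site shares, role shares and stratum effects, and the interim figures also on the variance used.

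**What to change.** 1. Add clinician role, as randomised, as a main effect in the final and interim models. Add site to the final model only, with small sites pooled by a rule fixed before unblinding. One workable rule merges sites with fewer than 5 first-attempt failures (arms combined), adding the next-smallest site until the group has 5. The threshold is a choice, but this rule left at most 0.04% of final fits inestimable; pooling sites under 50 subjects left 0.2–0.7%. Do not add site at the interim.
2. Make the synopsis and section 6.5 name the same interim logistic model, including the clinician-clustered variance.
3. State that the role-by-device interaction is fitted in a separate effect-modification model.
4. Report the standardised marginal odds ratio from the primary model. The adjusted coefficient is conditional, with a simulated median of 3.07–3.18 against the planned 2.98.

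**Cost.** SAP text and modest programming. No new data are needed, because site and role are recorded at randomisation. The downsides are:
- About 5–7 more parameters against 270 × 0.16 + 270 × 0.06 = 59.4 expected failures.
- With role at the interim, 0.2–2.1% of fits are inestimable, against 0.1% without.
- At 10 patients per clinician with an uncorrected sandwich, two-look null rejection moves from 0.055–0.063 to 0.059–0.064. A Kauermann-Carroll correction gives 0.053–0.054 to 0.055–0.057, so a small-sample correction should be specified; the power gain is then only about 0–0.2 points.
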